8.3 Crossover Between Study Arms

If a participant has or develops a contraindication to the specific drug they have been randomized to receive prior to discharge on EP (ie prior to initiation of the study intervention), they will be considered for crossover to the other arm and, if there is no contraindication to the other drug, can be switched to that arm. These instances and reasons for crossover will be documented. Crossover in this way will be allowed so that patients are not deprived of the standard of care anticoagulation after RC for their participation in the study and to better mimic the current prescribing patterns in which the drugs are frequently substituted for each other. Potential bias from allowing crossover is expected to be minimal as there is not a strongly plausible link between the contraindications to enoxaparin or apixaban and adherence to enoxaparin or apixaban. Furthermore, the contraindications to enoxaparin and apixaban are mostly quite rare; the only anticipated contraindication will be creatinine clearance (CrCl) <30 for enoxaparin. Any other possible indication for crossover will be reviewed by PI. Patients who crossover should still complete the study visits and both an intention to treat (ITT) and perprotocol (PP) analyses will be completed.

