9.3 Analysis of the Primary Endpoint

The primary objective of this study is to compare drug adherence between the two study arms, and the corresponding primary endpoint of the study is the proportion of days at home during which the participant took the prescribed anticoagulant. This is defined as the proportion of days covered (PDC).

PDC = number of days of anticoagulant actually taken / number of days of anticoagulant supposed to take

Number of days of anticoagulant actually taken is determined during the POD 30 phone call by asking the participant how many pills/vials they have remaining and then subtracting that from the size of the prescription they were given. Number of days of anticoagulant supposed to take is calculated by subtracting the number of days postop the patient was discharged from 30.

PDC will be compared between the two groups using a **non-inferiority trial design** with difference in proportions test with the following hypothesis:

H₀: Apixaban is inferior to Enoxaparin in terms of the average PDC response.

HA: Apixaban is non-inferior to Enoxaparin in terms of the average PDC response.

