9.4 Analysis of Secondary Endpoints

The following secondary endpoints will be assessed to further characterize adherence and also related elements of satisfaction and cost, though analyses of these related elements are not dependent on findings of the primary endpoint.

- 1. A binary measure of adherence: adherent vs non-adherent. Adherent is defined as taking *all* intended anticoagulant. Adherence in this definition will be compared using a test of proportions (proportion of patients in one study arm that were "adherent" vs proportion of patients in the other arm that were "adherent") within the ITT and population.
- 2. Cost of the medication. There are several measures of cost that will be studied as endpoints, including overall medication cost, cost paid by insurance, and most importantly participant out of pocket cost. Cost will be measured in dollars and reported as median and as mean depending on the presence of outliers. This will be collected from pharmacy review of prescriptions. Cost will be compared using a rank sum test.
- 3. Scores on the two validated questionnaires given: PROMIS and COST. These validated questionnaires both have scoring systems and a t test of the average score of participants in each arm will be compared (ie average score on COST for participants in apixaban arm vs average score on COST for participants in enoxaparin arm). A rank sum test will be used if distributions have outliers.

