9.6 Analysis of Safety Endpoints

Given the well-established safety profile of both drugs and their use as SOC after cystectomy there is no formal safety endpoint for this study. However, both bleeding and VTE events will be solicited and tracked (see section 7) for safety analysis. DVT, PE, and a composite

outcome of the two will be compared between the two study arms using a test of proportions. For bleeding events, medical review of the chart by an investigator will determine if the event is Major, Clinically Relevant Non-Major (CRNM), or Minor (see section 7) and these three outcomes will be compared between the two groups as well as a composite outcome of Non-Minor Bleeding (Major and CRNM) using test of proportions.

These as well as any other adverse events will be graded (see section 7) and presented in a descriptive way with any further detail deemed clinically relevant by the PI (including but not limited to the treatment and outcome of the AE) included.

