9.7 Populations for Analyses

The analysis of primary endpoint, PDC, as well as analyses comparing the results of the questionnaires will be conducted using an Intention-to-Treat (ITT) Dataset consisting of all randomized participants. We expect minimal crossover after randomization however if there is significant crossover we would also perform the analysis in an "As Treated" (AT) dataset consisting of participants categorized to the drug they ultimately received after crossover. Cost analyses will be performed using a dataset of all prescriptions (there may be more than one prescription per participant if there is crossover between study arms, though again this is expected to be minimal). Safety analyses will be performed in the ITT dataset as well as in participants who meet criteria for "adherent" to their anticoagulant (as defined above in section 9.4). Missing data will be assumed random and discarded from all analyses; missing data is expected to be low as there are only two study visits.

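### The repeat safety comparison in adherent participants (section 9.7) tests between arms in a post-randomisation set that a clot or bleed can itself remove people from; it should be descriptive and supportive only

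*Combined protocol and SAP*

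**What the plan says.** Section 9.7 sets two populations for safety: "Safety analyses will be performed in the ITT dataset as well as in participants who meet criteria for" adherence, with a pointer to the definition in section 9.4. That definition is strict: "Adherent is defined as taking *all* intended anticoagulant". Section 9.4 does not say how intended is counted. The only count in the document is the PDC denominator in section 9.3: "Number of days of anticoagulant supposed to take is calculated by subtracting the number of days postop the patient was discharged from 30". The numerator comes from the pills or syringes left at the POD30 call. Randomisation takes place at discharge (section 4.1), so membership of the adherent set is settled only afterwards.

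Section 9.6 says that "there is no formal safety endpoint for this study" but still plans between-arm testing. For VTE, DVT, PE and a composite "outcome of the two will be compared between the two study arms using a test of proportions". For bleeding, "these three outcomes will be compared between the two groups as well as a composite outcome of Non-Minor Bleeding (Major and CRNM"). That is seven outcomes, at the two-sided 0.05 level set in section 9.1.

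Section 8.2 lists a blood clot, a bleeding event and other adverse events among the anticipated reasons for a clinician to stop the anticoagulant. It says a clot would require leaving the prophylactic dose; section 7.4.1 says only that VTE may lead to this. Section 8.2 also requires the date and reason of every discontinuation to be recorded.

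**The concern.** The adherent set is defined by the trial's primary outcome, which the synopsis expects to differ between the drugs. The safety event can also decide who belongs to it. Nothing in 9.6 or 9.7 exempts the set from the tests or labels it supportive.

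A reader of the resulting table would naturally take it as the event rate in people who took the drug in full. On the 9.3 count it would leave out participants whose clot or bleed ended their treatment before POD30, and it would attach p-values to a comparison that is no longer between randomised groups.

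**Working it through.** The plan gives no figure for this analysis, so there is nothing to reproduce. The check follows the definitions and then sizes the effect under stated assumptions.

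**Step 1: how an event changes membership.** A participant discharged on day D has 30 − D intended days (9.3). If a clot or bleed stops the drug before POD30, doses are left over, the count falls short of 30 − D, and the participant is not adherent under 9.4. The event leaves the set with the participant. Exclusion is not automatic: events after POD30, bleeds with no missed dose, and dose changes on the same drug can all stay in.

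**Step 2: pre-POD30 VTE on the 9.3 count.** Let p be the true pre-POD30 risk and s the share of events that stop the drug and leave doses over. The documents do not give s. Assume that other non-adherence is unrelated to VTE risk. Then

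rate in adherent set = p(1 − s) / (1 − ps).

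Section 2.1 gives 5% for a cystectomy series on 28 days of enoxaparin, without a time window, and 2–12% for symptomatic VTE in the first 30 days after surgery. The second range starts at surgery, so it includes inpatient events.

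| True p | s = 25% | s = 50% | s = 75% |
|---|---|---|---|
| 2% | 0.0150/0.9950 = 1.5% | 0.0100/0.9900 = 1.0% | 0.0050/0.9850 = 0.5% |
| 5% | 0.0375/0.9875 = 3.8% | 0.0250/0.9750 = 2.6% | 0.0125/0.9625 = 1.3% |
| 12% | 0.0900/0.9700 = 9.3% | 0.0600/0.9400 = 6.4% | 0.0300/0.9100 = 3.3% |

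If 5% is instead the risk to POD90 and half the events precede POD30 (assumed), the rate is (0.05 − 0.025s)/(1 − 0.025s) = 4.4%, 3.8% or 3.2%.

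**Step 3: between arms.** Suppose both arms have a true 5% but s is 100% in one and 50% in the other (assumed). The adherent set shows 0% against 0.025/0.975 = 2.6%, a difference made by selection alone.

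**Step 4: if intended days end at the stop date.** The forced exclusion disappears. What remains depends on when doses are missed. Assume 60% are perfect over 24 days, a 5% risk, and every event stopping the drug at day 12. Let q be the chance that an event case still qualifies; the rate is 0.05q/(0.05q + 0.95 × 0.6).

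- Misses at a constant daily rate: q = 0.6^(12/24) = 0.775, rate 6.4%.
- Half of non-adherers never start: q = 0.8 × 0.75^(12/24) = 0.693, rate 5.7%.
- All non-adherers never start: q = 0.6, rate 5.0%, no bias.

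**Step 5: bleeding.** Full adherers have more exposure, which pulls the other way. Assume 6% overall and 40% full adherers with twice the risk of the rest. Others: 0.06/(0.4 × 2 + 0.6) = 4.29%; adherers: 8.57%. Applying the Step 2 formula with p = 8.57% gives 6.6% at s = 25% and 4.5% at s = 50%, on either side of 6%.

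**Step 6: what the test could show.** Section 9.3.1 plans 45 analysed per arm. With 60% adherent (assumed) that is 27 per arm, with 27 × 0.05 × (1 − s) = 1.0, 0.7 or 0.3 pre-POD30 VTE events left at s = 25%, 50% or 75%. A pooled two-sided z test gives p = 0.075 for 0 against 3 events and p = 0.038 for 0 against 4. Fisher's exact test needs 0 against 6 (p = 0.023; 0 against 5 gives 0.051).

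**The case against.** The strongest reply is that little depends on this table. Section 9.6 disclaims a formal safety endpoint, section 3 makes VTE and bleeding tertiary, the synopsis concedes limited power, and the ITT comparison is planned alongside. All of that stands and is why the point is minor. It does not justify testing in this set. The low power makes the tests easy to give up.

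A second reply is that intended in 9.4 need not follow the 9.3 denominator. That also stands: 9.4 does not cite 9.3, and a stop-date reading would remove the forced exclusion. A reader might then infer that the bias simply reverses and inflates the rate. The documents do not support that. Step 4 gives anything from no bias upward, depending on the pattern of missed doses, and the barriers in section 2.1 (cost, coverage, refusal of injections) make never starting plausible. On either reading the set is not randomised.

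A third reply is that an as-treated grouping is no more randomised than the adherent set. This is correct, so such a table can be offered only as supportive. Section 8.3 also promises a per-protocol analysis that 9.7 never defines, and the adherent set is the nearest thing to one for safety. Any change should settle that too.

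Finally, the synopsis speaks of contributing events from both arms to possible meta-analysis. A reader might infer that the pooled evidence would be distorted. The text does not say that the adherent subset would be supplied, and ITT counts would be available.

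**Conclusion.** The point holds and is minor. As written, the plan lets a clot or bleed before POD30 remove the participant from the set in which that outcome is compared, and then applies between-arm tests there. For pre-POD30 VTE, on the 9.3 count, the adherent-set rate is likely too low: a true 5% would show as 3.8% to 1.3% for s between 25% and 75%. Those sizes rest on assumed values of s and on other non-adherence being unrelated to VTE risk. The direction for bleeding is not determined, nor is the size of any bias if intended days end at the stop date.

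Two further inferences should be resisted. One is that every early VTE must drop out: 7.4.1 says only that VTE may end the intervention, and a participant with no doses left over would still count as adherent. The other is that the ITT safety analysis is thereby shown to be sound. This particular selection does not affect it, but 9.7 also discards missing data as random, and that was not examined here.

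**What to change.** In section 9.7:

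1. Name ITT as the main safety analysis.
2. Present the adherent-set safety table descriptively, with no between-arm tests, labelled supportive.
3. Report by arm how many participants, with which events, were excluded because a clot, bleed or other adverse event stopped the drug. Section 8.2 already has the dates and reasons documented.
4. State how intended days are counted for this table.
5. Optionally, add a supportive as-treated safety table: participants with at least one dose after discharge, grouped by the drug first taken after discharge, with events counted regardless of later stopping or switching. State that this is not a randomised comparison either. First taken matters because 9.7 groups "participants categorized to the drug they ultimately received after crossover", crossover under 8.3 happens "prior to discharge on EP (ie prior to initiation of the study intervention"), and 8.2 notes that a clot may lead to a change of anticoagulant. Reconcile this table with the per-protocol analysis promised in 8.3.

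The cost is a few sentences and no new data. The tested adherent-only comparison is lost, but it has almost no power at this sample size. With the minimal crossover that 9.7 expects, an as-treated table would probably look much like ITT.

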2.3 Preliminary Institutional Results

Given the earlier data suggesting barriers to adoption include cost, we sought to assess the state of prescription costs at our institution and determine how likely this is to pose a barrier to patient adherence. We reviewed our institution's outpatient pharmacy data from July to December of 2022, including the copays that patients being discharged on prophylactic dose apixaban and enoxaparin face at our institution as well as difficulties encountered with prior authorizations. Data suggest that copays may vary from as low as \$0 to >\$100, and that copays are much more likely to be increased with apixaban (Table 1). Review of prior authorizations show that a substantial number of prior authorizations were submitted, and in particular that denial of these prior authorizations and insurance coverage may pose a problem for both medications, in particular apixaban (Table 2).

Table 1. Patient copays for Enoxaparin and Apixaban

Lovenox PX (30mg & 40mg QD	
Copay (\$)	Count
0	103
0-20	108
21-50	27
51-100	14
>100	17
Total	269

Apixaban PX (2.5mg BID)		
Copay (\$)	Count	
0	15	
0-20	14	
21-50	11	
51-100	3	
>100	4	
Total	47	

Table 2. Outcomes of prior authorizations submitted for Enoxaparin and Apixaban

Prior Authorizations					
Medication	Approved	Denied	Total		
Apixaban	32	9	41		
Lovenox	19	2	21		

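### Section 9.7 commits to no VTE or bleeding analysis by drug actually received, so a crossover participant's at-home events count under a drug they were not discharged on

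*Combined protocol and SAP*

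**What the plan says.** Section 9.7 (Populations for Analyses) deals with the datasets in this order.

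- Adherence and questionnaires: the set is the "Intention-to-Treat (ITT) Dataset consisting of all randomized participants". The sentence that introduces it is limited to these endpoints and does not mention safety.
- As Treated: "if there is significant crossover we would also perform the analysis in an 'As Treated' (AT) dataset", made up of "participants categorized to the drug they ultimately received after crossover". No threshold for the amount of crossover is given.
- Safety: "Safety analyses will be performed in the ITT dataset as well as in participants who meet criteria for" being adherent. Section 9.4 defines that as having taken all of the intended anticoagulant. The As Treated set is not mentioned in this sentence.

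Section 9.6 compares DVT, PE, their composite and the bleeding categories between the two study arms with tests of proportions.

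Section 8.3 allows crossover to the other drug before discharge if the assigned drug is contraindicated, and states that "the only anticipated contraindication will be creatinine clearance (CrCl) <30 for enoxaparin". It promises both ITT and per-protocol analyses for crossover, but names no endpoint for either. Section 9.7 defines no per-protocol set.

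Synopsis objective 4 is to collect safety and efficacy data on the two drugs. It concedes that the study is too small to detect differences and offers the data for possible meta-analysis.

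**The concern.** The safety objective is about the drugs, but the committed analyses are by allocation or in a subset chosen by adherence. For someone who changes drug before going home, allocation and exposure are different things. A bleed on apixaban in a participant randomised to enoxaparin is reported as an enoxaparin bleed.

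The second safety set is not a substitute. It is selected on behaviour after randomisation that the safety event itself can change, and the plan does not say whether it is grouped by randomised arm or by drug taken.

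What is at stake is the labelling of a small number of events in tables that later meta-analyses may take at face value.

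**Working it through.** **1. Which set gives safety by drug received?**

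| Set | Where | Grouped by | Covers safety? | Condition |
|---|---|---|---|---|
| ITT | 9.7 | randomised arm | yes | none |
| Adherent | 9.7, 9.4 | not stated | yes | all intended drug taken |
| As Treated | 9.7 | drug received | not stated; follows the adherence and questionnaire sentence | crossover judged significant, undefined |
| Per-protocol | 8.3 | not defined | no endpoint named | none stated |

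No row is grouped by drug received, covers safety and is unconditional.

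**2. Timing.** Section 8.3 crossover comes before discharge. Section 10.4 starts the adverse-event period at discharge. A crossover participant therefore has no at-home event time on the randomised drug, and under ITT every at-home event is counted under the other drug.

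**3. The adherent set.** Section 8.2 lists a bleeding event and a blood clot among the anticipated reasons for a clinician to stop the anticoagulant. Section 9.3 counts intended days as 30 minus the postoperative day of discharge. If intended is read that way in Section 9.4, a participant who stops early because of a bleed has not taken all intended drug and leaves the set, taking the event with them.

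**4. Size of one event.** The plan states no crossover rate and no expected bleeding rate, so there is no plan figure to reproduce. Enrolment is 108 (synopsis, Section 5.3). If all are randomised 1:1, n = 108/2 = 54 per arm.

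- One event is 1/54 = 1.85 points of an arm's rate.
- Moving it from one arm to the other changes the difference by 2/54 = 3.7 points.
- Moving the participant as well changes the denominators to 53 and 55. With no other events, the apixaban-minus-enoxaparin difference goes from -1/54 = -1.85 to +1/55 = +1.82 points, again a shift of about 3.7.
- With the 45 per arm planned for analysis, the shift is 2/45 = 4.4 points.

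**5. How likely is such an event?** The figures here are assumptions: m participants move from enoxaparin to apixaban, with an event rate r on apixaban of 2% to 10%. The only general range in the documents is for VTE, 2-12% in the 30 days after surgery (Section 2.1). It is not a bleeding rate and is not restricted to the time after discharge.

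Expected misattributed events = m × r. Chance of at least one = 1 − (1 − r)^m. For the last column I assume true rates of 5% on enoxaparin and 10% on apixaban, with switchers at the same risk as others on apixaban. The ITT difference is then (10 − 5) × (1 − m/54) points.

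| Switchers of 54 | Expected events, r = 2% to 10% | Chance of at least one | ITT difference (true 5.0) |
|---|---|---|---|
| 1 (2%) | 0.02 to 0.10 | 2% to 10% | 4.9 |
| 3 (about 5%) | 0.06 to 0.30 | 6% to 27% | 4.7 |
| 5 (about 10%) | 0.10 to 0.50 | 10% to 41% | 4.5 |

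At 10% crossover or less, at most half an event is expected to be misattributed. When one is, it moves the observed difference by 3.7 points.

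**The case against.** The case for leaving the plan alone is reasonable. ITT preserves the randomised comparison. Randomisation takes place at discharge (Section 4.1), so the window for a Section 8.3 crossover is short. Section 5.2 already excludes conditions that preclude either drug, which narrows the renal route. Section 9.7 expects minimal crossover. Safety is tertiary (Section 3), Section 9.6 sets no formal safety endpoint, and events will also be described individually. The As Treated and per-protocol wording does not expressly rule out safety. All of this stands, and it limits the size of the problem. It does not supply a committed analysis by drug received.

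Three stronger readings are tempting, and the documents do not support them.

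- **Switching will be common.** Section 8.3 refers to "current prescribing patterns in which the drugs are frequently substituted for each other", and Section 2.3 says that "denial of these prior authorizations and insurance coverage may pose a problem for both medications, in particular apixaban". Table 2 shows 9 of 41 apixaban requests denied (22%) against 2 of 21 for enoxaparin (10%). The first remark describes general practice, not an expected rate in the trial. Denial is not a named crossover route: Section 8.3 concerns contraindications and sends other indications to the PI. Participants fill the prescription at their own cost (Section 6), so a denial may lead to payment or to no drug. The data come from one institution, are not described as cystectomy-only, and do not show whether denied prescriptions are among the Table 1 counts. No switch rate can be derived from them.
- **Participants who never take drug are charged to the wrong drug.** They are not. Under ITT they stay with their own assigned drug, and the adherent set omits them.
- **ITT necessarily pulls a bleeding difference towards zero.** It does so in the table above, where switchers carry ordinary risk. If they are selected for low creatinine clearance, the direction is not assured.

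**Conclusion.** The gap is real and modest. Followed as written, the plan produces no assured table of VTE and bleeding by the drug participants went home on. Neither committed safety set fills that place: ITT labels crossover participants by allocation, and the adherent set can drop those whose event made them stop.

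It would go too far to say that safety is never examined by drug taken. The As Treated set is conditional and the per-protocol promise names no endpoint, so the text is ambiguous rather than an exclusion.

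The expected distortion is small if crossover is as rare as the plan expects. The 3.7-point shift is the consequence of one misattributed event, not a forecast that one will occur, and it rests on all 108 enrolled being randomised; consent is preoperative, so fewer may be. The event and crossover rates used above are assumptions. Sample size, power and alpha are unaffected. The point deserves a correction before data are seen because events will be few and the results are offered for pooling.

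**What to change.** In Section 9.7:

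1. Add a safety set, whatever the amount of crossover: participants with at least one post-discharge dose, grouped by the drug actually received at discharge. Report bleeding and VTE in it beside ITT.
2. List participants who took no dose separately, by assigned drug.
3. Report events after a post-discharge change of drug or dose separately. Section 8.2 foresees such changes after a clot, and assigning later bleeds to whatever drug was in use at onset would put therapeutic-dose events into a prophylaxis comparison.
4. Report events from POD31 to POD90 separately. Screening continues to POD90 (schema), but prophylaxis ends at POD30.
5. State how the adherent set is grouped, and that it is supportive only.
6. Reconcile the per-protocol analysis of Section 8.3 with the As Treated set of Section 9.7, naming the endpoints that each covers.

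The cost is a paragraph and one extra table. Crossovers and their reasons are already documented under Section 8.3, dates and reasons for discontinuation under Section 8.2, and use of at least one dose follows from the POD30 medication count. Where that count is missing, exposure should be shown as unknown.

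The drawback is that the by-drug comparison is not purely randomised. For example, participants with low creatinine clearance may move to apixaban with no counterpart moving the other way. ITT should therefore stay alongside it.

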6 STUDY INTERVENTION

Both enoxaparin and apixaban are FDA approved in the setting of VTE prophylaxis and considered standard of care for EP after radical cystectomy. Study personnel will not be directly providing or administering either drug. Rather, the study intervention is the randomization to receive a prescription (with standard clinical counseling) for either of the two forms of prophylaxis. The participant will then be responsible for filling the prescription at their own cost and self-administering the anticoagulant, as would be standard of care after a radical cystectomy. The anticoagulants will be prescribed according to the clinical standard of care: 40 mg injected subcutaneously once daily for enoxaparin and 2.5 mg tablet taken orally twice daily for apixaban. Doses may be reduced in increased based on the patient's medical comorbidity profile (for example weight and CrCl) according to standard prescribing practices. Regardless of the time of day of discharge, participants will be instructed to start self-administering the medication the day after discharge, and continue through post-op day 30.

Participants who fail to receive a prescription for either anticoagulant will be considered not to have received the study intervention. Participants who receive the prescription but report poor compliance with the prescription have still received the study intervention; their poor compliance is tracked as the primary outcome of the study.

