7 STUDY ASSESSMENTS

At the time of enrollment, participants will be offered to complete the Demographics questionnaire either in person (if applicable), via phone (if applicable), or via a secure REDCap link emailed to them.

Participants will be contacted via phone on POD30 and POD90. During the phone call, participants will be given the option to receive an email with a secure link to REDCap to complete the majority of the study visit electronically (PMAS, Patient Satisfaction, and COST

questionnaires). Medication counting and screening for adverse events including VTE and bleeding must be done over the phone rather than via emailed link.

Study assessments will be conducted by staff other than the treating physician, and staff members will clearly state the contact is part of the research study, not part of routine clinical care.

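### The primary PDC analysis is labelled ITT but discards missing counts as random; no planned analysis tests that assumption, and the count is not protected after a drug stop

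*Combined protocol and SAP*

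**What the plan says.** Section 9.7 places the primary endpoint and the questionnaire comparisons in an "Intention-to-Treat (ITT) Dataset consisting of all randomized participants". The same paragraph then states: "Missing data will be assumed random and discarded from all analyses". Its only support is that "missing data is expected to be low as there are only two study visits".

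The endpoint has a single source. Section 9.3 says that the days taken are "determined during the POD 30 phone call by asking the participant how many pills/vials they have remaining", and section 7 says "Medication counting and screening for adverse events including VTE and bleeding must be done over the phone rather than via emailed link". Section 6 retains participants who received a prescription and complied poorly: "their poor compliance is tracked as the primary outcome of the study".

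Section 8.2 covers participants who must stop the anticoagulant. Whether they remain, and which parts of the visits they complete, is left to the PI, depending on the reason for stopping and on how long they had followed the protocol. Section 7.4.1 says that a VTE may end the study intervention but does not end study participation. Section 8.2 also defines loss to follow-up as a visit not completed after three contact attempts, and requires the date and reason of every discontinuation to be documented. Section 4.1 makes the trial open-label.

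**The concern.** The ITT label and the discard rule cannot both describe the primary analysis once a count is missing. Among poor compliers, those reached by phone are kept and scored low, while those not reached are deleted as if at random. The justification in 9.7 concerns how much will be missing, not why.

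Section 8.2 adds a second route to missing counts. Time on protocol is closely tied to PDC, and an unblinded PI may use it in deciding what a participant completes.

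Non-inferiority is judged on the between-arm difference in PDC. Loss that is related to adherence and unequal between arms therefore moves the estimate relative to the margin. Documented reasons would let unequal loss be seen, but no planned analysis would say whether it changes the conclusion.

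**Working it through.** **Is the assumption tested anywhere?** No imputation, worst-case or tipping-point analysis is planned. The as-treated analysis in 9.7 ("if there is significant crossover we would also perform the analysis in an" as-treated dataset) and the per-protocol analysis in 8.3 both address crossover, not missing counts.

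**Is there a planned missing-data rate to reproduce?** No; 9.7 gives none. Section 5.3 enrols 108 to analyse 90, and (108 − 90)/108 = 16.7%. This is not a missing-outcome rate. Enrolment is before surgery (5.3) and randomisation is at discharge (4.1), so part of the allowance is used before randomisation. For the same reason 108/2 = 54 randomised per arm is an upper limit.

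**How much could informative loss matter?**

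From the documents: enoxaparin PDC 85%, margin 15 points and one-sided 0.05 (9.3.1). Assumed: a true difference exactly at the margin (apixaban 70%), 54 randomised per arm, uncounted participants 40 points below their own arm's mean, and the missing shares below. Two variances are used. Section 9.3 names a "difference in proportions test with the following hypothesis", which implies a binomial variance. The alternative is a continuous PDC with an assumed SD of 0.25, which is not in the documents.

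1. Bias in an arm with share m missing = m/(1 − m) × gap. At 5%: 0.05/0.95 × 0.40 = 0.0211. At 10%: 0.10/0.90 × 0.40 = 0.0444. With a 20-point gap these halve to 0.0105 and 0.0222.
2. Counted per arm: 54 × 0.95 ≈ 51; 54 × 0.90 ≈ 49.
3. P(false non-inferiority) = Φ((bias in apixaban − bias in enoxaparin)/SE − 1.645).

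For 10% missing on apixaban and 5% on enoxaparin, informative in both, the net bias is 0.0444 − 0.0211 ≈ 0.0234 before rounding.

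- Binomial: observed means 0.744 and 0.871. SE = √(0.744 × 0.256/49 + 0.871 × 0.129/51) = 0.078. Φ(0.0234/0.078 − 1.645) = 0.089.
- SD 0.25: SE = 0.25 × √(1/49 + 1/51) = 0.050. Φ(0.0234/0.050 − 1.645) = 0.120.

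| Missing counts (40-point gap) | Binomial | SD 0.25 |
|---|---|---|
| 10% apixaban, 5% enoxaparin, informative in both | 8.9% | 12.0% |
| 5% apixaban, 10% enoxaparin, informative in both | 2.6% | 1.7% |
| Equal share, informative in both | 5.0% | 5.0% |
| 5% in each arm, informative in apixaban only | 8.3% | 11.1% |
| 10% in each arm, informative in apixaban only | 13.7% | 22.2% |
| 5% in each arm, informative in enoxaparin only | 2.8% | 1.9% |
| 10% in each arm, informative in enoxaparin only | 1.4% | 0.6% |

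With a 20-point gap the first row becomes 6.7% and 7.9%.

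**What would a count after a clinician-directed stop mean?** The denominator in 9.3 is 30 minus the postoperative day of discharge, with no adjustment for stops. Take discharge on day 14, the latest allowed: the denominator is 30 − 14 = 16. A stop ordered halfway through scores 8/16 = 50%, the same as a participant who simply gave up. Collecting these counts without settling their scoring would leave the endpoint ambiguous for the very participants concerned.

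**The case against.** The strongest reply is that loss after randomisation may be small. There are only two calls, three contact attempts are made, and section 10.7 pays participants at one site for completing both visits. These measures should reduce loss, but they do not test whether what remains is random.

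Three stronger readings are tempting, and the documents do not support them.

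- **That the plan is biased towards apixaban.** Direction is not established. Section 2.2 cites a retrospective cohort with more compliance events on enoxaparin (33.5% against 0%), and 2.1 reports reluctance to inject. Sections 1.1 and 2.3 raise cost and coverage problems with apixaban. Loss related to adherence on enoxaparin alone makes the test conservative. The largest figures in the table need a mechanism confined to apixaban, for which the documents give no reason.
- **That about 17% of outcomes will be missing.** This treats the enrolment allowance as missing counts, although some of it precedes randomisation.
- **That 8.2 drops the count after a drug stop.** It does not say so. Stopping the drug is not among its listed reasons for complete discontinuation from the study, and the text can be read consistently with 7.4.1. What stands is that 8.2 leaves the matter to discretion and does not protect the count.

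**Conclusion.** The point holds as a worthwhile, inexpensive improvement. As written, the primary analysis is complete-case under an untested missing-at-random assumption, for an endpoint whose collection may depend on the behaviour it measures. Section 8.2 leaves part of that collection to an unblinded PI.

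On the assumed inputs, moderately unequal loss (10% against 5%) moves the false non-inferiority rate from 5% to about 9% to 12%, or down to about 2% to 3% if the imbalance is reversed. Equal loss has no effect on it. These figures rest on an assumed 40-point gap, assumed missing shares and at most 54 randomised per arm; they show sensitivity and do not predict what will happen. That missing the call relates to adherence is a judgement, since the documents contain no data on who completes the count.

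**What to change.** 1. **Section 8.2:** state that the day-30 count is attempted, at the call already planned, for every randomised participant whatever their treatment status, with no PI discretion over collecting the primary outcome. Keep the three-attempt rule. Reconcile 8.2 with 7.4.1.
2. **Section 9.3:** state in advance how days after a clinician-directed stop enter the PDC denominator.
3. **Section 9.7:** keep the complete-case primary analysis, call it that, and state that it assumes data missing at random. Add one pre-specified delta (tipping-point) analysis of the PDC difference, varied separately by arm, against the 15-point margin. Report missing counts and reasons by arm.

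The cost is protocol wording and modest extra analysis; no additional participants or visits are needed. The downside is that the conclusion may prove less robust than the complete-case result suggests. The tipping-point rule must be fixed before data are seen, and counts not attempted at day 30 cannot be recovered later.
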